6.4 Missing Data

If numerical values are missing but characteristic values are not missing because some signs, namely < and >, are included in the characteristic values, the numerical values will be imputed following the below rules:

- If '<' is included in the characteristic value, a smaller value between the value without < or the lower range value will be imputed,
- If '>' is included in the characteristic value, a greater value between the value without > or the upper range will be imputed.

If the information of year or month is missing for duration of VVA, 0 will be imputed for calculating summary statistics but kept missing for listings.

Other missing data will not be imputed. All analyses will be based on observed data.

6.5 Pooling of Small Centers

The study will be conducted under the same protocol across all the study centers. It is anticipated that some centers will not enroll a sufficient number of subjects. To ensure estimable results, small centers will be pooled. Centers with less than 40 subjects will be combined with other centers prior to breaking the blind. Centers with 40 or more subjects may also be pooled if necessary, so that the size of the pooled centers is consistent with the size of the larger centers. The pooling will be done by geographical location if possible. These pooled centers will be used in the analyses model, not the individual centers.

7 DEMOGRAPHIC AND OTHER BASELINE CHARACTERISTICS

7.1 Subject Disposition and Discontinuation

The number of subjects who failed at Screening Period will be summarized along with the reasons for failure.

The following analyses will be performed for randomized subjects. Treatment group will be defined as randomized.

Among subjects randomized to each treatment group, the number and percentage of subjects who complete Visit 5, prematurely discontinue before Visit 5 and continue taking medications after Visit 5 will be summarized. In addition, reasons leading to study discontinuation before Visit 5 and after Visit 5 will be summarized for each treatment group. We confirmed all subjects, whose discontinuation reason is entered as 'other' after Visit 5, discontinued the study because of the protocol amendment.

The number and percentage of randomized subjects included in each analysis population and the reasons for excluded subjects will also be presented.

7.2 Demographic and Baseline Characteristics

The distribution of demographics and baseline characteristics shown in Table 3 will be described for the ITT Population by treatment group. Summary statistics will be calculated for quantitative scale items, and frequency and proportion of subjects in each category will be obtained for ordered and qualitative (i.e., binary and nominal) scale items. Quantitative scale items for age and body mass index (BMI) will be categorized and tabulated by treatment group.

For the ITT Population, medical history will be summarized by treatment group. The medical histories will be classified by System Organ Class (SOC) and preferred term (PT), using the Medical Dictionary for Regulatory Activities (MedDRA). MedDRA Version 18.0 will be used.

Table 3 Demographic and Baseline Characteristics

Quantitative scale items	Age, height, body weight, BMI, duration of VVA
Binary or nominal scale items	Ethnicity, race, uterus, current hot flashes, previous hormone treatment, severity of vaginal dryness

BMI = body mass index;

See Section 12 for category.

8 STUDY CONDUCT

8.1 Protocol deviation

Subjects with major protocol deviations will be listed.

8.2 Treatment Exposure and Compliance

Summary statistics of number of days of treatment exposure and treatment compliance rate will be summarized by treatment group based on electronic data capture (EDC) data.

Number of days of treatment exposure is defined as ‘actual days of correctly dosed.’
The dosing period during which a subject takes medication as follows:

$\{(\text{End date of dosing}) - (\text{initial dose date}) + 1\}$ [days]
for subjects who withdraw the study before Visit 5.

$\{(\text{Date of Visit 5}) - (\text{initial dose date}) + 1\}$ [days]
for subjects who complete the study or take medication beyond Visit 5.

Treatment compliance rate is defined as:

$100\{(\text{actual days of correctly dosed}) / (\text{duration of treatment exposure})\}$ [%].

Data until Visit 5 in ITT and Safety populations will be analyzed.

The same analysis for after Visit 5 will also be performed for Safety Population. For this analysis, subjects who continue to Part B in the previous protocol and continue taking study medication after Visit 5 will be included.

Furthermore, categorized duration of treatment exposure and treatment compliance rate will be summarized by treatment group (see Section 12 for category).

8.3 Prior and Concomitant Medications

Prior and concomitant medications will be coded using the World Health Organization (WHO) Drug Dictionary, March 2015. Prior medication is defined as all medications taken before Day 1 of study medication. If the medication was provided more than 6 months prior to screening and the start date is missing, the drug will also be classified as a prior medication. Concomitant medication is defined as all medications taken at Day 1 or later. If the medication was still ongoing at the end of the study and the end date is missing, the drug will be classified as a concomitant medication. A medication can be classified as both prior and concomitant.

Concomitant medication will be summarized as follows.

- if a subject takes study medication for more than 12 weeks (beyond Visit 5), concomitant medications that will be taken until Visit 5 will be summarized;
- if a subject takes study medication for 12 weeks or less than 12 weeks, concomitant medications taken up to 14 days from the last dose will be summarized .

For ITT Population, the number and percentage of subjects who take prior and concomitant medications will be summarized by preferred name for each treatment group.

All prior and concomitant medications will be listed.

If a subject has more than 1 medication that are coded as the same preferred name, the subject will be counted only once for that preferred name.

If the medication cannot be classified into concomitant medication or prior medication based on the above definitions due to a partial missing date, the rules below will be applied for the classification of the medication.

For start date:

- If the year and month are observed but the day is missing, the first day of the month will be used.
- If the year is observed but the month is missing, the first day of the year, 1st January, will be used.

And, for end date:

- If the year is missing and it is not ongoing, the concomitant medication should be treated as an ongoing treatment.
- If the year and month are observed but the day is missing, the last day of the month will be used.
- If the year is observed but the month is missing, the last day of the year, 31st December, will be used.

The imputed dates will not be displayed in the listings.

9 EFFICACY

All of efficacy endpoints described below will be summarized using descriptive statistics. The subject who doesn't have a baseline value or any post baseline values for a specific parameter will be excluded from the analysis.

9.1 Primary Efficacy Analysis

9.1.1 Primary Efficacy Endpoint

The primary efficacy endpoints will be the difference between ospemifene 60 mg QD and placebo in treatment of VVA due to menopause in women with moderate to severe vaginal dryness as the MBS of VVA at 12 weeks based upon:

- Change from baseline in percentage of parabasal cells in the maturation index to Week 12

- Change from baseline in percentage of superficial cells in the maturation index to Week 12
- Change from baseline in vaginal pH to Week 12
- Change from baseline in severity of MBS of vaginal dryness to Week 12

The definition of baseline is described in the Section 6.3.

9.1.2 Statistical Analysis Methods for Primary Efficacy Endpoint

The following analyses will be performed for both of ITT and PP Populations. For each of percentage of parabasal cells, percentage of superficial cells and vaginal pH, mixed-effects model for repeated measures (MMRM) approach will be used. In the model, repeated measurements of the change from baseline at Week 4, Week 8, and Week 12 will be the response variable. Treatment, week, treatment by week interaction and study center will be fixed effects. Baseline value will be modeled as covariates. Significance test to compare the ospemifene group with the placebo group will be based on the mean difference between the two groups at Week 12.

SAS code to the above model is as follows:

```
proc mixed data=DRYDATA;
  class USUBJID TREAT CLUSTER WEEK;
  model CHG = TREAT BASE CLUSTER WEEK TREAT*WEEK/ ddfm=kenwardroger;
  repeated WEEK/subject=USUBJID type=un;
  estimate 'Treatment Group Difference at Week12'
    TREAT 1 -1 TREAT*WEEK 0 0 1 0 0 -1;
run;

CLUSTER: Pooled center
CHG: Change from baseline to each week (4w,8w,12w)
```

For the MBS of vaginal dryness, generalized estimating equations (GEE) model will be used to fit a marginal proportional odds model to the longitudinal ordered categorical data [1]. In the model, repeated measurements of the change from baseline in MBS of vaginal dryness at Week 4, Week 8, and Week 12 will be the response variable. Treatment, week, treatment by week interaction and study center will be fixed effects. Baseline severity of dryness will be modeled as covariates. Significance test to compare ospemifene group with the placebo group will be based on the mean of cumulative log odds ratio (over ordered category responses) at Week 12.

SAS code to the above model is as follows:

```
proc genmod data=DRYDATA;
  class USUBJID TREAT CLUSTER WEEK;
  model CHG = TREAT BASE CLUSTER WEEK TREAT*WEEK/
  dist=multinomial link=clogit type3 aggregate=TREAT;
  repeated subject=USUBJID/type=ind;
  estimate 'Treatment Group Difference in Mean of Cumulative Log Odds Ratio at Week12'
    TREAT 1 -1 TREAT*WEEK 0 0 1 0 0 -1 / exp;
run;
```

CLUSTER: Pooled center
CHG: Change in intensity of dryness from baseline to each week (4w,8w,12w)

In order to evaluate the robustness of the GEE analysis for the MBS of vaginal dryness, a sensitivity analysis using MMRM method described above will be performed. In this analysis, ordered categorical data will be treated as continuous data.

9.2 Secondary Endpoints That Will Be Analyzed Inferentially

9.2.1 Endpoints That Correspond to the Primary Efficacy Endpoints, but Done at Week 4 and Week 8 Rather Than at Week 12

- Change from baseline in percentage of parabasal cells to Week 4 and to Week 8
- Change from baseline in percentage of superficial cells to Week 4 and to Week 8
- Change from baseline in vaginal pH to Week 4 and to Week 8
- Change from baseline in severity of MBS of vaginal dryness to Week 4 and to Week 8

For percentage of parabasal cells, percentage of superficial cells and vaginal pH, same MMRM model as in 9.1.2 will be used. Significance test to compare the ospemifene group with the placebo group will be based on the mean difference between the two groups at Week 4 and at Week 8.

For MBS of vaginal dryness, same GEE model as in 9.1.2 will be used. Significance test to compare ospemifene group with the placebo group will be based on the mean of cumulative log odds ratio (over ordered category responses) at Week 4 and at Week 8.

9.2.2 Severity of VVA Symptoms Other Than Vaginal Dryness

Change from baseline in the following VVA symptoms to Week 4, Week 8, and Week 12.

- Vaginal and/or vulvar irritation or itching
- Difficult or painful urination
- Vaginal pain associated with sexual activity
- Vaginal bleeding associated with sexual activity

Same GEE model as in 9.1.2 will be used. The analysis population will be subjects whose baseline values are moderate or severe in ITT for this analysis.

9.2.3 Change From Baseline in Maturation Value to Week 4, Week 8, and Week 12

Maturation value (MV) is defined as follows:

$MV = (S \times 1) + (I \times 0.5) + (P \times 0)$, where

- MV = Maturation value
- S = % of superficial cells
- I = % of intermediate cells

- P = % of parabasal cells

Analysis of Covariance (ANCOVA) will be used for observed case data for Week 4, Week 8, and Week 12, respectively. Baseline MV will be included as covariate.

9.2.4 Percentage of Subjects Who are Responders at Week 4, Week 8, and Week 12

A subject is defined as a responder if all the following conditions are met:

- MV increase of at least 10 from baseline
- Vaginal pH decrease of at least 0.5 from baseline
- Improvement (decrease in severity) of at least 1 point in the most bothersome symptom of dryness from baseline

Fisher's exact test will be used for observed case data for Week 4, Week 8, and Week 12, respectively.

9.2.5 Change from Baseline in Vaginal Health Index to Weeks 4, 8, and 12

Vaginal Health Index (VHI) consists of 5 items: (1) overall elasticity; (2) fluid secretion; (3) pH; (4) epithelial mucosa; and (5) moisture. Each item consists of 5 categories with scores 1 to 5, the better the each item, the greater the score. Add scores of 5 items to obtain the total score. If any item score is missing, the total score will be missing.

Change from baseline in the total score will be analyzed using ANCOVA for Week 4, Week 8, and Week 12, respectively. Baseline score will be included as covariate.

9.2.6 Change from Baseline in Vulvar Health Index to Weeks 4, 8, and 12

Vulvar Health Index (VuHI) consists of 7 items: (1) labia majora; (2) labia minora; (3) clitoris, (4) introitus and elasticity; (5) color; (6) discomfort and pain; and (7) other findings (petechiae, excoriation, ulceration, etc.). Each item will be assessed on a 4-point scale (0 = normal, 1 = mild, 2 = moderate, and 3 = severe). Add scores of 7 items to obtain the total score. If any item score is missing, the total score will be missing. For (6) discomfort and pain, the severity data will be derived from VVA symptoms "vaginal pain associated with sexual activity", and apply with the 4-point scale score.

Change from baseline in the total score will be analyzed using ANCOVA for Week 4, Week 8, and Week 12, respectively. Baseline score will be included as covariate.

9.2.7 Change from Baseline in Vulvo-vaginal Imaging to Week 12

From vaginal imaging, 9 parameters {Labia Majora, Labia Minora, Clitoris, Urethra, Introitus and Elasticity, Color, Erythema, Moisture, Other Findings (Petechiae, Excoriation, Ulceration, etc.)} will be assessed. These items are evaluated as 4 categories with scores 0 to 3 by 3 independent reviewers. The median value evaluated from 3

reviewers will be used for analyses. Add scores of 9 items to obtain the total score. If any item score is missing, the total score will be missing.

Change from baseline (Randomization) to Week 12 in the vaginal imaging total score will be analyzed using ANCOVA. Baseline score will be included as covariate.

The visit window for valid image is ± 14 days from targeted visit dates.

The data will be collected as optional parameters.

9.2.8 Change from Baseline in Total Score and Each Domain Score of the Female Sexual Function Index Questionnaire to Weeks 4, 8, and 12

Category score of patient's response to each of 19 questionnaires is presented in Appendix 2. The individual domain scores and total score of the Female Sexual Function Index (FSFI) can be derived from the computational formula outlined in the table below. For the domain scores, add the scores of the individual items that comprise the domain and multiply the sum by the domain factor. Add six domain scores to obtain the total score.

Table 4 Female Sexual Function Index Scoring System

Domain	Questions	Score range	Factor	Minimum score	Maximum score
Desire	1,2	1-5	0.6	1.2	6
Arousal	3,4,5,6	0-5	0.3	0	6
Lubrication	7,8,9,10	0-5	0.3	0	6
Orgasm	11,12,13	0-5	0.4	0	6
Satisfaction	14,15,16	0 (or 1) - 5	0.4	0.8	6
Pain	17,18,19	0-5	0.4	0	6
Total Score				2.0	36

If the response to any question within an individual domain is missing, that domain score will be missing. If any domain score is missing, the total score will be missing.

Change from baseline in the total score and the domain scores will be analyzed using ANCOVA for Week 4, Week 8, and Week 12, respectively. Baseline score will be included as covariate.

9.2.9 Change from Baseline in Urinary Symptoms to Weeks 4, 8, and 12

Urinary symptoms will be assessed as absent or present using the Urinary Distress Inventory (UDI-6). The symptoms include: (1) frequent urination; (2) urine leakage related to the feeling of urgency; (3) urine leakage related to physical activity, coughing, or sneezing; (4) small amounts of urine leakage; (5) difficulty emptying bladder; and (6) pain or discomfort in the lower abdominal or genital area. When a symptom is present,

the degree a subject is bothered will be rated on a 4-point scale. In the analysis, the following category score will be used.

- 0 : the symptom is absent
- 1 : the symptom is present, however not bothers her at all
- 2 : the symptom is present and bothers her slightly
- 3 : the symptom is present and bothers her moderately
- 4 : the symptom is present and bothers her greatly

Add scores of 6 items to obtain the total score. If any item score is missing, the total score will be missing. If the data is missing for a symptom is present or not but the degree is entered, the individual score and the total score will be calculated.

Change from baseline in the total score will be analyzed using ANCOVA for Week 4, Week 8, and Week 12, respectively. Baseline score will be included as covariate.

9.2.10 Change From Baseline in Markers of Bone Metabolism to Week 12

On bone resorption, the following markers will be measured:

- Serum N-telopeptide of type 1 collagen (NTX)
- Serum C-terminal telopeptide of type 1 collagen (CTX)
- Serum bone sialoprotein (BSP)
- Urinary deoxypyridinoline (DPD)
- Serum tartrate-resistant acid phosphatase 5b (TRACP-5b)

On bone formation, the following markers will be measured:

- Serum total alkaline phosphatase
- Serum bone-specific alkaline phosphatase (BSAP)
- Serum amino-terminal propeptide of type 1 collagen (P1NP)
- Serum osteocalcin

Change from baseline to Week 12 and to Week 12/ET in each marker will be analyzed using ANCOVA. Baseline value will be included as covariate.

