9.4 Handling of Missing Data

Missing data will not be imputed. All analyses will be based on observed data.

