4.2 Study Blinding and Randomization

After screening, subjects who have $\leq 5\%$ superficial cells in the maturation index of the vaginal smear, a vaginal pH > 5.0 and vaginal dryness as MBS of VVA based on self-assessment, who also meet all other eligibility criteria, will be randomized in a 1:1 ratio to receive either ospemifene 60 mg QD or matching placebo for 12 weeks.

Randomization will be stratified by severity of MBS of vaginal dryness at Visit 2 and by the presence or absence of the uterus. Randomization of subjects without a uterus will be limited to 60% of the study population.

This study will be conducted in a double-blind manner using a placebo matching the test drug in appearance, labeling, and packaging. All subjects, the investigator, all study personnel, and the sponsor will be blinded to the treatment assigned at randomization until database lock.

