6.2 Statistical Testing

All statistical tests will be performed at the 0.05 significance level using two-sided tests, except where otherwise noted.

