6.3 Study Day and Analysis Windows

Day 1 is the initial dose date for subjects. Previous day to Day 1 is expressed as Day -1, and days before Day -1 in Screening Period are expressed as Day -2, Day -3, ... , etc.

Allowance window for each of the scheduled visits is shown in Table 1.

Allowance window for diary data is shown in Table 2.

If more than one visit occurs during a visit window, the one closest to the target day will be assigned to the visit. If two visits are equidistant from the target day, the latter visit will be assigned to the visit for post-baseline values.

If a subject discontinues from the study, the data obtained at early termination visit will be treated as one visit data based on the allowance windows.

Table 1 Definition of Visit Window

Scheduled Visit	Target Day	Window (Days)
Visit 1	Day -28	≤ Day -1
Visit 2 (Day 1)	Day 1(Randomization)	Day 1
Visit 3 (Week 4)	Day 29	Day 16 to Day 43
Visit 4 (Week 8)	Day 57	Day 44 to Day 71
Visit 5 (Week 12)	Day 85	Day 72 to Day 99
Early termination	Last dosing date	+ 14

Table 2 Definition of Diary Data Window

Week	Daily Data	Weekly Data (Target Day)
Week 1	Day 1 to Day 7	Day 4 to Day 10 (Day 7)
Week 2	Day 8 to Day 14	Day 11 to Day 17 (Day 14)
Week 3	Day 15 to Day 21	Day 18 to Day 24 (Day 21)
Week 4	Day 22 to Day 28	Day 25 to Day 31 (Day 28)
Week 5	Day 29 to Day 35	Day 32 to Day 38 (Day 35)

Week	Daily Data	Weekly Data (Target Day)
Week 6	Day 36 to Day 42	Day 39 to Day 45 (Day 42)
Week 7	Day 43 to Day 49	Day 46 to Day 52 (Day 49)
Week 8	Day 50 to Day 56	Day 53 to Day 59 (Day 56)
Week 9	Day 57 to Day 63	Day 60 to Day 66 (Day 63)
Week 10	Day 64 to Day 70	Day 67 to Day 73 (Day 70)
Week 11	Day 71 to Day 77	Day 74 to Day 80 (Day 77)
Week 12	Day 78 to Day 84	Day 81 to Day 87 (Day 84)

Assessments that occur more than 14 days after the last dose of study medication will be excluded from the above visit windows.

The baseline is defined as the last value that is observed prior to the first dose of study medication. For a variable that is planned to be observed at screening and randomization, the data at randomization will be used as baseline. For such variable, if the data at randomization is missing for a subject, the data observed at screening will be used as baseline.

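### The responder endpoint is tested with an unstratified Fisher's exact test on observed cases: valid but conservative, it ignores the randomization strata, and its data rule can bias the comparison if dropout differs by arm and is related to response

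*SAP*

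**What the plan says.** SAP 9.2.4 defines a composite: "A subject is defined as a responder if all the following conditions are met". The conditions are a rise of at least 10 in maturation value, a fall of at least 0.5 in vaginal pH, and an improvement of at least one point in dryness. On the test it says "Fisher's exact test will be used for observed case data for Week 4, Week 8, and Week 12, respectively". SAP Table 5 lists this as a secondary analysis in the ITT population, with no model.

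On missing data, SAP 6.4 says "Other missing data will not be imputed. All analyses will be based on observed data", and Protocol 9.4 says "Missing data will not be imputed. All analyses will be based on observed data". For women who stop early, SAP 6.3 says "the data obtained at early termination visit will be treated as one visit data based on the allowance windows", with windows of Day 16 to 43, Day 44 to 71 and Day 72 to 99 for Weeks 4, 8 and 12. It adds: "Assessments that occur more than 14 days after the last dose of study medication will be excluded from the above visit windows".

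On the design, SAP 4.2 says "Randomization will be stratified by severity of MBS of vaginal dryness at Visit 2 and by the presence or absence of the uterus". The responder test uses neither factor.

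Three things are not stated: how to classify a woman with one component missing, any missing-data sensitivity analysis for this endpoint, and a risk difference with a confidence interval. The endpoint is also absent from Protocol 9.10.2, and SAP section 13 does not record it as a change.

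**The concern.** Table 5 labels the population ITT, which SAP section 5 defines as every randomized and dosed woman. Under observed cases the denominator is smaller: women with an assessable response in the visit window. A response rate among assessable women and one among treated women can differ, and so can the two treatment differences.

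The test raises a separate question. Fisher's exact test conditions on the margins and, with about 300 women per arm, rejects less often than the nominal 5%. Randomization was stratified by two factors, yet the comparison makes no use of them.

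This is the SAP's only efficacy endpoint that combines cytology, pH and symptom within one woman, so it is likely to be quoted as a response rate. What is at stake is the accuracy of that rate and difference, plus some power. The co-primary result is not at stake.

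**Working it through.** **Inputs from the documents.** About 300 women per arm, 1:1 (Protocol 9.2, SAP 4.3); two-sided 0.05 (SAP 6.2: "All statistical tests will be performed at the 0.05 significance level using two-sided tests, except where otherwise noted"); four strata from two binary factors (SAP 4.2). **Assumed, because the documents give none:** response rates and dropout by arm.

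**The plan's own figure.** No power is stated for responders. The stated power of at least 90% for the co-primaries reproduces. For dryness, effect size 0.27 with 300 per arm gives Φ(0.27 × √150 − 1.96) = Φ(1.347) = 0.911. The other three endpoints are at about 1.00, so the product under independence is about 0.91.

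**1. Size and power of Fisher's test** (exact enumeration, 270 per arm, i.e. 10% missing):

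| True rates | Fisher | Pearson chi-square |
|---|---|---|
| 5% in both arms | 0.0325 | 0.0491 |
| 10% in both arms | 0.0361 | 0.0496 |
| 20% in both arms | 0.0393 | 0.0504 |
| 18% vs 10% (power) | 0.73 | 0.77 |
| 30% vs 12% (power) | 0.9993 | 0.9995 |

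The loss is about 4 points at a moderate difference and disappears at a large one.

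**2. Fisher against stratified CMH** (20,000 simulated trials per row, 300 per arm, four equal strata, control rate 23% to 25%, treatment odds ratio 1.6):

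| Log odds ratio of severity / uterus | Fisher size | CMH size | Fisher power | CMH power | Gain (points) |
|---|---|---|---|---|---|
| 0 / 0 | 0.041 | 0.052 | 0.700 | 0.733 | 3.2 |
| 0.4 / 0.2 | 0.039 | 0.051 | 0.685 | 0.721 | 3.6 |
| 0.7 / 0.4 | 0.038 | 0.051 | 0.681 | 0.723 | 4.2 |
| 1.1 / 0.7 | 0.035 | 0.051 | 0.652 | 0.714 | 6.1 |

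The first row shows that about 3 points come from Fisher's own conservatism. The remainder comes from leaving out prognostic strata. Type I error is not inflated in any row.

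**3. The observed-case rule.** Suppose all missing women are non-responders, the response rate among all treated women is p in both arms, and dropout is d. The observed-case rate is then p/(1 − d). At 15% dropout on ospemifene and 5% on placebo (255 and 285 observed):

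- p = 20%: 23.53% − 21.05% = 2.48 points; Fisher rejects in 9.8% of trials.
- p = 30%: 35.29% − 31.58% = 3.72 points; 13.8%.
- p = 40%: 47.06% − 42.11% = 4.95 points; 20.1%.

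At 10% versus 5% the false difference is 1.17 to 2.34 points, with rejection in 5.7% to 8.3%. At 10% in both arms there is no false difference and rejection is 3.9% to 4.2%. Swapping the arms' dropout reverses the sign. If dropout is unrelated to response (255 and 285 observed, equal rates), there is no bias and Fisher's size is about 4.4%.

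Running Pearson's test on the same 15%/5% data rejects in 10.2%, 15.0% and 21.2% of trials. The inflation therefore comes from the data rule and would remain under a different test.

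**4. When there is a real difference.** With observed-case rates of 40% vs 20% (20 points), counting missing women as non-responders gives 40(1 − d₁) − 20(1 − d₂):

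- 10%/10% dropout: 36 − 18 = 18
- 15%/5%: 34 − 19 = 15
- 10%/15%: 36 − 17 = 19
- 5%/15%: 38 − 17 = 21

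**The case against.** A reader might infer that the plan favours whichever arm has more dropout. The documents do not support that. They give no dropout by arm, and the bias needs missing women to be less likely responders. Step 4 also has a case (10%/15%) in which ospemifene is overstated although placebo loses more women. Nor is the fall from 20 to 18 points at equal 10% dropout evidence of favouring an arm: both rates shrink by the same factor and their ratio is unchanged.

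A reader might also blame Fisher's test for the dropout bias. Step 3 shows otherwise: the test is valid, and its conservatism works slightly against a false positive.

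Nor does the SAP say that a woman missing any one component is dropped. It states such a rule for VHI, VuHI, imaging, FSFI and UDI-6, but not in 9.2.4. A woman with one observed failed component is already a certain non-responder. Early stoppers are partly kept too: Protocol 8.5 collects symptoms, pH and smear at early termination, and SAP 6.3 assigns them to a visit window.

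The remaining objections are fair and limit the point. Observed-data analysis is the prespecified rule for the whole study, so changing 9.2.4 alone would contradict SAP 6.4 and Protocol 9.4. Counting a woman with a lost smear as a failure has its own bias. The endpoint is secondary. None of this supplies the missing rule for partly missing components or the missing sensitivity analysis, nor gives a reason to leave the strata unused.

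**Conclusion.** The point holds in two limited parts.

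- **Efficiency.** Fisher's test has a true size of about 0.03 to 0.04 and leaves out both strata. The cost against stratified CMH is about 3 to 6 power points at an odds ratio of 1.6 from a control rate of 23% to 25%, and close to zero at 30% vs 12%.
- **Conditional bias.** The observed-case comparison is distorted only if dropout differs by arm and is related to response, or if the intended estimand counts missing women as failures. The 2.5 to 5.0 points and 10% to 20% false positives belong to an assumed 15% vs 5% dropout with every missing woman a non-responder. If dropout is small and balanced, or unrelated to response, little or nothing changes.

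This is a worthwhile, low-cost correction to a secondary analysis. No co-primary conclusion depends on it.

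**What to change.** Before unblinding:

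1. In SAP 9.2.4 and Table 5, replace Fisher's test with a CMH test stratified by baseline dryness severity (moderate/severe) and uterus status, and report a stratified risk difference with its 95% CI.
2. State that a woman with at least one observed failed component is a non-responder at that visit, whatever else is missing.
3. Add an ITT analysis that counts women without an assessable response as non-responders, shown beside the observed-case result.
4. Record item 3 as an exception in SAP 6.4, and in the opening of SAP section 9, which excludes women without baseline or post-baseline values. List it in SAP section 13 as a deviation from Protocol 9.4 with its reason, as Protocol 9.1 requires.

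The cost is SAP wording and a small amount of programming, since both strata are already collected for randomization. Response rates in the added analysis will be slightly lower, and it understates response if missingness is unrelated to outcome. That is why the observed-case result should stay beside it. Item 2 also lets partly observed women enter the observed-case table only as failures, which a footnote should say.
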